### **Resting State EEG and treatment outcome prediction**

**Rationale:** Our previous work showed that network modularity derived from a form of resting state fMRI was predictive of changes in cognitive functioning from training (Arnemann, 2015). Using a data driven network analysis approach, we propose to evaluate the potential use of EEG biomarkers for predicting the cognitive gains that individuals achieve through training. This will be the first study to apply the graph theoretic metric of network modularity using EEG recordings in participants with TBI.

**Experimental EEG Design:** Same task as described in Preliminary Study #3.

**Statistical Analysis:** The first stage will identify possible EEG biomarkers (frequency band, connectivity metric) using a Spearman Correlation with attention/executive function behavioral measures (baseline and change due to training). We will employ a stepwise regression to create a model from the potential biomarkers that maximizes the explanation of variance in behavioral measures.

**Predicted Results:** *Building on our past observations from MRI functional connectivity, we predict that patients with high modularity, and low characteristic path length, will exhibit the greatest positive behavioral changes with training, and these differences between subjects will be greatest in the theta and alpha bands. Patterns of connectivity in previously reported EEG measures suggest higher modularity scores in mTBI patients than controls (Cao & Slobounov, 2009), and that disruptions in long distance connectivity are primarily in the theta and alpha bands (Kumar et al., 2009). The study will allow a dual approach, combining data-driven analysis of resting state EEG data to identify potential predictive markers, and hypothesis-driven testing of cognitive performance to explain the relation of these biomarkers to the variability in response to training. This approach allows us to develop a model of brain connectivity on baseline resting state data, and test it on tasks that engage working memory and attention processes. We further hypothesize that pre-training resting state modularity and CPL scores in mTBI patients will predict the degree to which theta and alpha power during working memory tasks normalize towards control responses.*

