There is significant variability in response to any given rehabilitation intervention, and the neural bases of this variability are not well understood. Electroencephalography (EEG) is a research tool with an established history of clinical application following TBI (Rapp et al., 2015; Schmitt & Dichter, 2015). Previous reports of mild to moderate TBI have suggested alterations in the theta (4-8 Hz) and alpha (8-13 Hz) ranges (Thornton & Carmody, 2009). Given its availability in clinical settings, and utility in measuring the effects of attention and working memory (Luck et al., 2000), we propose to examine the neurophysiologic underpinnings of behavioral responses to training using well-validated event-related EEG markers, and novel application of EEG network connectivity measures to resting state data. In a related example, EEG markers for Attention-Deficit Hyperactivity Disorder (ADHD) suggested that processing deficits in the encoding and maintenance stages of working memory (WM) are differentially explained by variance in theta and alpha (Lenartowicz et al., 2014). Application of these methods to understand and even predict treatment outcomes could help direct interventions, save time, and improve patient quality of life. Better understanding the neural bases of functional improvements may help guide intervention development by providing new markers for feedback or targets for electrical modulation.

We will use a novel combination of neurocognitive training and two categories of EEG data for these investigations. (a) Event related changes in brainwaves can dissociate components of working memory into discrete processes that are targeted by training (attention, encoding, maintenance). We will examine EEG with WM load under distraction pre- and post-training, and test whether these markers help to explain neural bases of variability in behavioral changes with training. We predict that training-induced changes in

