quantified by computing mean amplitudes in defined latency windows relative to a 100 ms pre-stimulus baseline. The primary measure will be the ERP “old/new effect” elicited during memory retrieval, time-locked to probe onset. This will be quantified by subtracting mean amplitude for Old – New probes (300-500 ms post-stimulus) at midline electrodes (Honzel et al., 2014).

**EEG Time-Frequency and Network Analysis:** Off-line analysis for resting state and dual task data will be performed in the EEGLAB Matlab toolbox (Delorme & Makeig, 2004). Data will be filtered with bandpass limits of 0.1 to 55 Hz using a standard FIR filter and re-referenced to the average of mastoid electrodes. Periodic artifacts, such as eyeblinks, will be removed using the Infomax Independent Component Analysis (ICA) algorithm. Remaining data will be further band filtered into four frequency bands (theta: 4-8 Hz, alpha: 8-13 Hz, beta: 15-30 Hz, & gamma: 30-55 Hz), and power envelope and phase angle will be extracted with a Hilbert transform.

Resting state connectivity will be calculated over two second epochs using a graph theoretical approach comparing each pair of electrodes in each frequency band, based on correlation of band power changes, and degree of phase coherence. *As we are working with resting state data, we have no a priori hypothesis about directionality of information flow. Therefore, correlations of these measures will suffice (Bastos & Schoffelen, 2016), thereby decreasing computation demands.* Spurious connectivity will be corrected by eliminating neighboring electrode connections and ignoring electrode pairs with 0 degrees of phase lag. Remaining electrode pairs will be adjusted to a common threshold to control number of network connections across patients. From these binarized connectivity matrices, modularity and characteristic path length (CPL) will be calculated using the Matlab toolbox, EEGNET (Hassan, et al. 2015). Time-frequency responses to dual task conditions will be calculated using Hilbert transformed data, epoched and averaged over the same time window and baseline as ERP analysis.

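### The resting EEG screen never compares modularity and path length with band power from the same recording, so a positive result may not be separable from a power effect

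*Combined protocol and SAP*

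**What the plan says.** Under Resting State EEG and treatment outcome prediction, Statistical Analysis, the plan has two stages. First: "The first stage will identify possible EEG biomarkers (frequency band, connectivity metric) using a Spearman Correlation", against baseline attention/executive scores and their change with training. Second: "We will employ a stepwise regression to create a model from the potential biomarkers".

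The markers are built under Research Design and Methods, EEG Time-Frequency and Network Analysis. In each of four bands, "power envelope and phase angle will be extracted with a Hilbert transform". Connectivity between electrode pairs is "based on correlation of band power changes, and degree of phase coherence". Spurious links are handled by "eliminating neighboring electrode connections and ignoring electrode pairs with 0 degrees of phase lag". Then "Remaining electrode pairs will be adjusted to a common threshold to control number of network connections across patients", and modularity and characteristic path length (CPL) are computed from the binarised graphs.

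For resting data, the envelope is used only to build connectivity. Theta and alpha power do appear elsewhere: as responses in the working-memory task, as possible task-based predictors, and as a task outcome that resting modularity and CPL are expected to predict. None of these compares a resting network marker with resting power.

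**The concern.** Connectivity is estimated from a rhythm recorded on top of background noise. Where the rhythm is weak relative to the noise, chance has more say in which pairs make the edge budget. The graph then looks more random and modularity drops, although the underlying network is unchanged. Removing neighbouring and zero-lag pairs deals with volume conduction, and matching the edge count deals with density. Neither deals with differences between people in signal-to-noise ratio.

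The plan itself makes power a plausible rival. It says earlier reports in mild to moderate TBI "have suggested alterations in the theta (4-8 Hz) and alpha (8-13 Hz) ranges", and these are the bands where it expects the network markers to work best. It also hypothesises that resting modularity and CPL will predict how task theta and alpha power normalise; a marker that carries resting power could then amount to power predicting power.

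At stake is the interpretation. The aim extends an fMRI finding about network organisation. If modularity stands in for band power, the marker may still predict gain, but the credit given to network organisation would be wrong.

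**Working it through.** **The plan's own figure.** The only sample-size figure is 13 per group for the ERP old/new effect. With difference 1.097, SD 0.956 and two-sided alpha 0.05 (assumed), a two-sample t test needs n = 12.96, so 13, with power 80.1%. It reproduces but has no bearing here. No sample size is given for the resting-state aim.

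**Inputs from the documents.** 64 channels; 2 s epochs; envelope correlation and phase coherence; neighbouring and zero-lag pairs dropped; equal edge counts; 20 trained participants.

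**Inputs assumed.** Recording length 180 or 300 s (the plan says several minutes); edge density 10%, 15% or 25%; near-zero lag below 5 degrees; four modules; within-module coupling 0.3 or 0.15; SD of log amplitude 0.25 or 0.5; alpha band only.

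**Step 1: does modularity follow power when every network is identical?** The planned pipeline was simulated with 120 people per setting, varying only band amplitude. Spearman correlation of modularity with log band power:

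| Condition | Envelope | Phase |
|---|---|---|
| Noise floor fixed, coupling 0.3 (10 settings) | 0.46 to 0.97 | 0.83 to 0.98 |
| Coupling 0.15, independent noise | -0.04 | 0.20 |
| Coupling 0.15, spatially smooth noise | 0.19 | 0.79 |
| Overall gain only, noise scales too (6 settings, both measures) | -0.20 to 0.17 | -0.20 to 0.17 |

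In one fixed-floor setting (15% density, 180 s, independent noise), mean phase modularity was 0.26 in the lowest power quartile and 0.64 in the highest.

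**Step 2: what does this do to the screen?** Suppose power correlates a with gain, modularity correlates b with power, and the network has no effect of its own. The implied modularity-gain correlation is a × b:

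- a = 0.4, b = 0.7: 0.28, significant in about 20% of trials at n = 20.
- a = 0.6, b = 0.9: 0.54, significant in about 65%.

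Partial Spearman on log power brings the rate to 5-7%. Running the full pipeline at coupling 0.3 with a fixed floor (4 settings) gave 18-35% (envelope) and 28-37% (phase) for a = 0.4. For a = 0.61, a value borrowed from the fMRI modularity result, it gave 38-74% and 63-79%. Adjusted rates were 4-6%. With a = 0 the unadjusted rate is 5%.

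**Step 3: multiplicity.** Four bands × 2 connectivity measures × 2 metrics = 16 markers. At the strictest Benjamini-Hochberg step, 0.05/16 = 0.0031, the 20-65% becomes about 3-26%.

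**Step 4: what adjustment costs.** Let the true marker-gain correlation be r = 0.6, with power related to gain only through the marker, and let m be the marker-power correlation. The partial correlation is r(1 - m²) / √[(1 - m²)(1 - r²m²)].

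- m = 0.7: 0.306 / √(0.51 × 0.8236) = 0.47
- m = 0.84: 0.177 / √(0.294 × 0.746) = 0.38
- m = 0.9: 0.114 / √(0.19 × 0.708) = 0.31

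At n = 20, power falls from about 76% unadjusted to about 49%, 33% and 26%.

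**Step 5: path length.** In a simpler simulation (spectral modularity, zero-lag rule not imposed), CPL moved with power in the same direction as modularity in all 12 settings at coupling 0.3. For phase coherence the correlations with power were 0.89 to 0.97 for modularity and 0.80 to 0.97 for CPL. Overall, CPL rose with modularity in most settings run. The stepwise stage was not simulated.

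**The case against.** A reader might infer that modularity generally tracks band power, so that any positive result is an artefact. The documents do not support this. They give no noise level, coupling strength, edge density or spread of power, and the dependence is absent or small in several plausible conditions (Step 1).

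Nor do they say that resting power predicts gain. The theta and alpha alterations are attributed to TBI, and every participant has TBI, so that statement says nothing about who among them improves. Without such a link the unadjusted test keeps its 5% error rate.

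A reader might also infer that a result matching the plan's full prediction would be explained by power. The plan predicts high modularity together with low CPL. In most simulated settings power pushed both up, so the artefact would usually contradict that joint pattern. A result on modularity alone is the exposed case.

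The 20-65% is for one uncorrected test. Sample Size Calculation promises 5% false discovery control for other design and subject factors; whether that reaches this screen is unclear. Finally, this is a pilot looking for possible markers, and a marker that shares variance with power can still be useful.

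All of this limits the size and reach of the concern. It does not supply the missing comparison: the sponsor cannot know beforehand which signal condition its recordings will meet. Even if the first stage were read as admitting band power as a candidate, stepwise selection is not a prespecified test of modularity given power.

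**Conclusion.** The concern holds in conditional form. The plan contains no comparison of resting network markers with resting power, and none of its connectivity corrections deals with between-person differences in signal-to-noise ratio. A pure power effect could therefore be reported as modularity predicting response.

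The 20-65% false attribution rate requires a noise floor that does not scale with power, detectable coupling, a modularity-power correlation of 0.7 to 0.9 and a power-gain correlation of 0.4 to 0.6. All four are assumptions. The fall to about 5-7% after adjustment is expected by construction, since power was made the only cause; it shows that the adjustment works, not that power is the cause in this trial. The defect concerns what a positive result can be said to mean, not whether a marker can predict. The change should be made, with medium confidence in the likely size.

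**What to change.** For each band, compute log resting power from the Hilbert envelope already planned, and enter it in the first-stage screen as a comparator marker. Report every modularity and CPL association with gain both unadjusted and adjusted for same-band power (partial Spearman, or power included in the regression), with confidence intervals, alongside the marker-power correlation.

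Where the estimate shrinks materially on adjustment, describe the marker as predictive but not separable from band power. Do not use significance after adjustment as a pass/fail rule: given the losses in Step 4, non-significance with 20 participants would not show that power is responsible. State in advance that high modularity with high CPL would itself suggest the artefact, and say whether the 5% false discovery rule covers this screen.

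The cost is one covariate already in the pipeline, one degree of freedom in each adjusted analysis, four more candidates in the screen (one per band), and some wording. Adjusted estimates will be imprecise, which is why both versions are reported.

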Baseline assessments of cognitive status and functioning, as well as EEG, will be conducted in weeks 1-2. Time commitment for baseline assessments is approximately 4-5 hours. Participants will then be assigned to (a) active training or (b) no training conditions in a pseudo-random order, matched across key demographic variables. The no training condition will serve to assess changes to EEG and other measurements with repeated testing in the absence of active training. This will lay a foundation for future studies that will incorporate an active comparison intervention.

Participants in active training will complete seven training sessions in weeks 3-10. Training sessions last 2 hours, and participants are requested to complete approximately 2.5 hours of additional skill practice over the course of each week outside of session (total  $\sim 4.5$  hours per week). The same overall training time will be targeted ( $\sim 32$  hours) for all individuals, although the training schedule will accommodate variations in individuals' schedules and availability over the course of  $\sim 8$ -10 weeks to maximize engagement. In the 2 weeks after training concludes, participants will complete a second round of assessments ( $\sim 3$ -4 hrs). Participants will be compensated \$20/hr for their time during the assessment portions of the study as well as for their travel expenses at \$0.55/mile for travel greater than 20 miles to and from the study site.

Enrollment will begin within 3 months of the initiation of the grant period, and continue through month 21. Data will be checked and pre-processed on a rolling basis and final analyses and reports will be completed in months 22-24.

**Training Intervention:** Training follows a manualized protocol, with seven in-person two-hour sessions (Loya et al., 2014; Rodriguez et al., 2014) and instructions to practice skill use while playing the Startup-to-CEO game for 30 minutes/day, five times per week, and to practice skill use within the context of their daily life. Game scenarios are utilized to highlight contexts where goal-directed functioning is susceptible to disruption and where skill use might be helpful. They further help facilitate discussions about skill application in personal life. In addition, twice weekly semi-structured phone check-ins are conducted to provide motivational support and reinforce skill use.

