**Sample Size Calculation:** We powered the study based on prior group differences (mtBI/PTS vs. Controls). We used data from the Sternberg task (Honzel et al., 2014) to obtain an estimate of the standard deviation of the ERP old/new effect, and expected effect size based on a mixed effects ANOVA (subject as random effect) with group as the sole explanatory variable. To estimate sample size, we used the two sample *t* test as an approximation to the mixed effects ANOVA and used the method of variance inflation to account for the additional subject factors (Hsieh et al., 2003). We powered based on the primary experimental question at 80% and will control false discovery rate at 5% (Benjamini & Hochberg 1995) at the time of analysis for tests of other design and subject factors. The Sternberg data showed a mean difference between the patient and control groups of -1.097 with residual error of 0.956 from the mixed effects ANOVA. Using these values in a two-sample *t* test for mean difference, to obtain 80% power we need a sample size of 13 per group. *This pilot study will allow us to collect data to inform power calculations for future studies.*’

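### Resting-EEG predictors are screened and stepwise-selected in the same participants, with no internal validation and no stated comparison with the untrained arm

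*Combined protocol and SAP*

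**What the plan says.** All references are to the combined protocol and SAP.

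- **Resting State EEG and treatment outcome prediction, Statistical Analysis.** Stage one looks for markers "using a Spearman Correlation with attention/executive function behavioral measures (baseline and change due to training"). Stage two is: "We will employ a stepwise regression to create a model from the potential biomarkers that maximizes the explanation of variance in behavioral measures". No screening threshold, stepwise entry or removal rule, or analysis set is given.
- **EEG Time-Frequency and Network Analysis.** There are four bands (theta, alpha, beta, gamma). Connectivity is "based on correlation of band power changes, and degree of phase coherence", and from the resulting matrices "modularity and characteristic path length (CPL) will be calculated".
- **Same resting-state section, Predicted Results.** High modularity and low path length should go with larger gains, and "these differences between subjects will be greatest in the theta and alpha bands". The authors also intend to develop a model on baseline resting data and "test it on tasks that engage working memory and attention processes".
- **Study design and participant flow.** "The no training condition will serve to assess changes to EEG and other measurements with repeated testing in the absence of active training". The resting-state analysis does not mention this arm. The only group comparison in an analysis section is for ERP amplitudes, with time-frequency responses following the same models.
- **Sample Size Calculation.** False discovery rate is held at 5% "at the time of analysis for tests of other design and subject factors". The study is described as a pilot.

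**The concern.** The aim stated in Background and Significance is to forecast who responds to training. Two features of the analysis prevent it from answering that.

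First, a model chosen because it fits these participants is judged by its fit to the same participants. Selection from 8 or 16 candidates with 20 people inflates R² and makes the nominal p values too small. Applying the model to working-memory tasks does not validate it, because those are further measurements on the same people.

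Second, a correlation between a marker and change in the trained arm mixes response to training with individual differences in retest gain. Alternate forms and retest norms, planned for the neuropsychological tests, reduce the average practice effect but not its variation between people. The untrained arm could separate the two, but the section does not use it. Because the pilot is meant to inform later power calculations, an inflated association could carry into the next study.

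**Working it through.** **The plan's own figure.** None is given for the marker analysis. The only sample-size figure, 13 per group, is for the ERP old/new effect. It reproduces: 1.097/0.956 = 1.147, and a two-sided 5% t test (level assumed) has power 0.766 at 12 and 0.801 at 13 per group. It says nothing about the marker model.

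**Inputs.** From the plan: 20 trained and 20 untrained participants, 4 bands, 2 network metrics, 2 connectivity definitions. Candidates: 4 × 2 = 8 if the connectivity definitions are merged, 4 × 2 × 2 = 16 if kept separate. Assumed because not stated: Spearman screen at p < 0.05, stepwise entry at 0.05 and removal at 0.10, normal data, correlation ρ between candidates of 0 to 0.7.

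**Screen alone.** With K independent null candidates, P(at least one p < 0.05) = 1 − 0.95^K.
- K = 8: 1 − 0.663 = 0.337.
- K = 16: 1 − 0.440 = 0.560.

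**Screen plus stepwise, no true association, n = 20** (10,000 replicates per row). A candidate must pass both the rank screen and the regression entry test, so rates are below those for the screen alone.

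| Candidates | ρ | P(a model) | P(R² ≥ 0.3) | Mean R² given a model |
|---|---|---|---|---|
| 8 | 0 | 0.240 | 0.097 | 0.306 |
| 8 | 0.3 | 0.215 | 0.084 | 0.300 |
| 8 | 0.5 | 0.188 | 0.073 | 0.295 |
| 8 | 0.7 | 0.141 | 0.055 | 0.295 |
| 16 | 0 | 0.423 | 0.194 | 0.322 |
| 16 | 0.3 | 0.368 | 0.163 | 0.316 |
| 16 | 0.5 | 0.289 | 0.124 | 0.306 |
| 16 | 0.7 | 0.208 | 0.089 | 0.305 |

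**Sensitivity to the assumptions.**
- Screen at 0.10 and entry at 0.15, 16 candidates: a model with p < 0.05 in 36% to 55%.
- Stepwise on 16 uncorrelated candidates with no screen: 58% to 75%, mean R² 0.40 to 0.50.
- All 40 participants, 0.05 thresholds: a model in 23% to 43%, mean R² 0.16 to 0.18.
- Screen under Benjamini-Hochberg at 5%, n = 20: a model in 4% to 6%, but mean R² of those that survive is 0.36 to 0.41.

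**Selection repeated inside leave-one-out** (500 noise data sets that gave a model per scenario, ρ = 0 and 0.5). Median cross-validated R² is −0.067 and −0.106 with 8 candidates, and −0.148 and −0.116 with 16. If total variation is taken about the full-sample mean, a model with no predictors scores 1 − (20/19)² = −0.108, so these values mean no predictive ability. Cross-validated R² is still 0.3 or more in 8% to 11% of these data sets.

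**Group comparison, 20 per arm, two-sided 5%.**
- Trained arm alone, true r = 0.5: atanh(0.5) × √17 = 0.549 × 4.123 = 2.265. Power is about Φ(2.265 − 1.96) = 0.62; simulation gives 0.640.
- Marker predicts retest gain equally in both arms (r = 0.5): the trained-arm test is still significant in 64%, the marker × group term in 5.4%.
- True r = 0.5 trained, 0 untrained: 0.549/√(2/17) = 0.549/0.343 = 1.60. Interaction power is about Φ(1.60 − 1.96) = 0.36; simulation gives 0.338, or 0.329 with baseline score in the model.
- At the r = 0.61 reported for fMRI modularity in Preliminary Studies, item 3: if equal in both arms, the trained-arm test is significant in about 85% and the interaction in 4.6%. If 0.61 against 0, interaction power is about 54%.

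**The case against.** The study is a pilot, the section speaks of candidate markers, and it does not say which R² or p value will be reported. That lowers the severity but corrects nothing, since no alternative to the in-sample fit is described.

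A baseline EEG marker could be read as a subject factor and so fall under the 5% false discovery rate. On that reading false models drop to about the nominal rate. The scope is ambiguous, and the R² of surviving models remains inflated.

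The authors predict both direction and bands. Under noise about a quarter of first-entered markers would match both (half the bands, half the signs), so noise would seem to confirm the stated prediction in roughly 4% to 6% of data sets with 8 candidates and 5% to 11% with 16. This is a fair limit on the headline rates, but it does not repair the R².

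If all 40 participants were used, apparent R² would be about half as large. That can apply to the baseline correlations, but gains from training exist only in the 20 trained.

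On the group comparison, the untrained data will be collected and nothing forbids using them. The equal-in-both-arms case is an assumption, and the interaction is poorly powered. All of that stands. It argues for reporting an estimate with its interval, not for leaving the comparison out.

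**Conclusion.** The concern holds. As written, the marker analysis gives an optimistic fit and cannot show that a marker predicts response to training rather than retest gain. With n = 20 and 0.05 thresholds, noise yields a model in 14% to 42% of data sets, depending on candidate count and correlation, with apparent R² near 0.3. The exact rates carry moderate confidence because thresholds and correlations are assumed. The direction of the bias does not depend on them. The two omissions, internal validation and a marker-by-group comparison, are clear from the text. Given the pilot status this should be corrected before analysis, but it does not threaten the study as a whole.

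**What to change.** 1. Keep the data-driven model as exploratory. State the candidate list (8 or 16), the analysis set, the screening and stepwise thresholds, and whether the 5% false discovery rate covers the screen. Repeat the whole screen and selection inside cross-validation. Report the cross-validated R², with a permutation p value for the entire procedure, in place of the in-sample R².
2. Test the predictors already hypothesised, theta and alpha modularity and path length, as a prespecified set under the 5% false discovery rate, with change in the attention/executive composite as outcome. That is 2 × 2 = 4 tests with one connectivity definition and 8 with both.
3. Fit a model in all 40 participants with baseline score, group, marker and marker × group. Rest any claim about training response on the interaction, given as an estimate with a confidence interval. The marker main effect should not be taken as evidence of training response.

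The cost is analysis wording and some computing time. Reported R² will be lower, and the cross-validated R² is itself noisy at n = 20, hence the permutation p value. Interaction power is only about 34% for r of 0.5 against 0, before any false discovery rate adjustment, so an inconclusive interval is likely even if the effect is real.

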**Dual-Task Condition (Sternberg Memory Task + Arrow Flanker):** Participants will be required to perform the arrow flanker task during the delay interval of the Sternberg memory task. Nine flanker trials begin 300 to 500 ms following the presentation of each memory set. The stimulus parameters are the same as for the single-task flanker. The Sternberg probe is then presented 500 ms following the final flanker trial, and participants respond to indicate whether this item was in the previous memory set.

**Statistical Analysis:** The ERP old/new effect will be analyzed using a mixed effects ANOVA controlling for task (single, dual), set size (one, four), and time point (pre, post). The primary neuropsychological outcome measures will be included in the models as appropriate to assess changes from pre- to post-training. To examine the effects of repeated testing, differences in ERP mean amplitudes between patient groups (trained, untrained), task, and set size will be also be tested using a separate mixed effects ANOVA to control for random effects due to subject. Pre/post differences in Sternberg WM accuracy will be tested using a hierarchical generalized linear model. Time-frequency responses will be analyzed with the same mixed and linear models, with separate calculations for each frequency band, and a repeated measures model including all frequency bands.

**Predicted Results:** We predict that Veterans who show cognitive gains with training (based on neuropsychological measures) will show an increase in the ERP old/new effect in the dual task condition. Additionally, as prior work has shown that WM impairment in ADHD is characterized by decreased levels of alpha power during encoding, and compensatory increases in theta during maintenance (Lenartowicz, et al. 2014), we predict that cognitive gains will be reflected by changes in theta and alpha power over frontal scalp. Importantly, we can determine with precise temporal resolution whether the neural manifestations of training improvements occur during WM encoding, maintenance, and/or retrieval. Additional analyses will determine whether these EEG markers can predict which patients will improve with training.

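### The resting-state prediction that theta and alpha matter most has no planned comparison between bands; one pre-specified contrast would supply it

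*Combined protocol and SAP*

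**What the plan says.** The prediction is under Predicted Results in the section Resting State EEG and treatment outcome prediction. Participants with high modularity and low characteristic path length are expected to gain most from training, and "these differences between subjects will be greatest in the theta and alpha bands".

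The Statistical Analysis paragraph of that section has two steps:
- "The first stage will identify possible EEG biomarkers (frequency band, connectivity metric) using a Spearman Correlation with attention/executive function behavioral measures", taken both at baseline and as change due to training.
- "We will employ a stepwise regression to create a model from the potential biomarkers", chosen to explain as much behavioural variance as possible.

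The candidates are defined under EEG Time-Frequency and Network Analysis. There are four bands ("theta: 4-8 Hz, alpha: 8-13 Hz, beta: 15-30 Hz, & gamma: 30-55 Hz"). Connectivity is computed in two ways, "based on correlation of band power changes, and degree of phase coherence". From the resulting matrices, "modularity and characteristic path length (CPL) will be calculated".

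A model spanning the bands does appear elsewhere. In the working memory experiment, time-frequency responses are analysed "with separate calculations for each frequency band, and a repeated measures model including all frequency bands". The plan does not extend that model to resting modularity or path length.

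**The concern.** The prediction is comparative: associations in theta and alpha should exceed those in beta and gamma. The planned steps estimate each association and then select among them. A correlation that passes a threshold in one band and misses it in another does not show that the two correlations differ. Being retained by a stepwise procedure does not show it either, because that procedure selects for explained variance and may drop a band merely because it overlaps with another.

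Without a planned comparison, the material at hand for judging the prediction is which bands were selected or ranked highest. A report could then describe a predictor as specific to theta and alpha when all four bands carry the same information.

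**Working it through.** **The plan's own figure.** The only power figure is 13 per group for the ERP old/new effect (Sample Size Calculation). With a difference of 1.097, a residual SD of 0.956, and two-sided alpha 0.05 (assumed, since alpha for this test is not stated), the exact two-sample t test needs 12.96, so 13, with power 80.1%. It reproduces, but it does not concern bands.

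**Inputs from the documents**
- Four bands, two connectivity measures and two graph metrics: 4 × 2 × 2 = 16 candidates per behavioural measure.
- 20 trained participants (Participants), the sample for change due to training.
- A prior brain-behaviour correlation of 0.61 from n = 11, using fMRI modularity (Preliminary Studies, item 3). By Fisher z, atanh(0.61) = 0.709 and SE = 1/√(11−3) = 0.354. The approximate 95% interval is 0.709 ± 1.96 × 0.354 = 0.02 to 1.40, or about 0.02 to 0.89 as a correlation.

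**Inputs assumed, because the documents do not give them**
- Screening threshold: two-sided p<0.05.
- True correlation with outcome: the same in all four bands, at 0.3 to 0.5, and also 0.61.
- Correlation between band metrics: 0.3 to 0.5.

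**Threshold at n = 20.** With t = 2.101 on 18 degrees of freedom, the critical correlation is 2.101/√(18 + 2.101²) = 0.44.

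**Simulation.** 20,000 multivariate normal data sets per setting, one graph metric, Spearman correlation per band. No band differs from any other, so any apparent specificity is chance.

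| Pattern | True correlation 0.3-0.5 | True correlation 0.61 |
|---|---|---|
| Some bands pass, others fail | about 48-78% | about 50-59% |
| Theta and/or alpha pass, neither beta nor gamma | about 13-20% | about 5-6% |
| Theta and alpha both pass, neither beta nor gamma | about 2-5% | – |

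With Benjamini-Hochberg applied across the four bands, the second row becomes about 8-14% (6% at 0.61). The third row becomes about 1-4% at 0.3-0.5.

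**Ranking alone.** With four exchangeable bands, the largest correlation falls in theta or alpha in 2/4 = 50% of trials, and theta and alpha take both top places in 1/6 = 17%. These follow from counting and do not depend on sample size.

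**Direct contrast.** Take the mean Fisher z in theta and alpha minus that in beta and gamma, at n = 20 and equal true correlations of 0.3-0.5. Its standard error is about 0.19-0.23, and the bootstrap 95% half-width is about 0.40-0.48. The interval excluded zero, in either direction, in about 4-8% of trials when all bands were equal.

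For scale, correlations of 0.61 against 0.30 differ by 0.709 − 0.310 = 0.40 in Fisher z, about one half-width. A related test, the Williams test for dependent correlations on band averages, had 58-91% power for that difference and 98-100% for 0.61 against 0, over the admissible between-band correlations from 0 to 0.7.

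**The case against.** Several points on the other side stand.

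- **The plan does look at bands together.** A reader might infer that every band is only ever tested alone. That is not so: the working memory experiment has an all-band repeated measures model, and the resting-state stepwise regression can hold several bands at once. The first concerns time-frequency responses, and the second contrasts nothing. The gap is therefore confined to the resting-state analysis.
- **No rule says that selection decides.** The documents do not state that the prediction will be judged by which bands pass, and they give no threshold. The percentages depend on an assumed 0.05 screen.
- **Chance seldom produces the full pattern.** A reader might infer that chance would often confirm the prediction. The prediction names theta and alpha together. Both passing alone occurs in only about 2-5% of trials, and the looser pattern falls to 5-6% if the true correlation is 0.61. The ranking figures of 50% and 17% say nothing about this sample size.
- **There is a 5% false discovery rate rule.** Sample Size Calculation applies it to tests of other design and subject factors. Its reach to this screen is unclear. It would reduce false selections but would not compare bands.
- **The work is exploratory.** The study describes itself as a pilot and this analysis as data-driven, and the sentence sits under predicted results rather than among the stated tests. That lowers the weight of the point but does not supply the comparison.

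**Conclusion.** The point holds for the resting-state analysis only, as a cheap improvement. A comparative prediction is stated in advance, and no planned analysis tests it.

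The firm part is the reading of the text and needs no simulation. The sizes are conditional on the assumed threshold, true correlations and between-band correlations. Under them a mixed pass/fail pattern across identical bands is common, a pattern favouring theta and/or alpha is occasional, and the complete predicted pattern is uncommon. The documents do not support saying that the plan ignores cross-band modelling altogether, or that chance would usually deliver the predicted result.

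**What to change.** In the Statistical Analysis paragraph of Resting State EEG and treatment outcome prediction, add one contrast for modularity and one for characteristic path length:

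1. Name the connectivity measure used. If both are kept, there are 2 × 2 = 4 contrasts; apply the 5% false discovery rate across them.
2. Define the contrast as the mean Fisher-z Spearman correlation with change in the attention/executive composite in theta and alpha, minus that in beta and gamma. Set the sign to the predicted direction, which is reversed for path length.
3. Give a 95% interval from a bootstrap that resamples participants.
4. Claim that theta and alpha on average exceed beta and gamma only if the interval excludes zero in the predicted direction. Otherwise report all four bands side by side with intervals and make no ranking.

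The cost is one further analysis on quantities already computed, with no extra data. There are two drawbacks. At n = 20 the contrast is imprecise, so the band-specific claim may have to be dropped. And because it averages, it cannot show that theta and alpha each exceed the other bands: a strong theta could hide a weak alpha.
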